This study is an open-label, single ascending dose study in healthy participants. Up to six cohorts of 6 participants each are planned where the participants within each cohort are expected to receive the same dose of study drug. A total of approximately 36 participants will be enrolled and each will receive a single dose of BMS-984923.

If the Maximum Tolerated Dose (MTD) is reached prior to the sixth cohort, the remaining participants may be enrolled to obtain further data at the tolerated dose levels. During this process, the Principal Investigator (PI) ([name]), the medical monitor, and the DSMB must agree to proceed with the study and escalate to the next dose cohort, independent of the influence of the IND holder ([name]) and in compliance with the management of the Conflict of Interest for [name]. The process is further described in Section 12 (Data and Safety Monitoring Plan). Briefly, a safety assessment will be completed and reviewed for all treated participants per cohort prior to opening enrollment into the next increased dose level.

The study periods protocol are as follows:

- **Screening:** (within 90 days prior to Day 1) Patients have 90 days from the time of signing informed consent to complete their screening assessments and, if needed, their washout period for prohibited concomitant medications. The screening laboratory tests must be completed within 30 days prior to Day 1.
- **Treatment period:** Day 1: Admission, administration of study drug, and 2 night in-patient stay; Day 3: Discharge following the completion of all scheduled procedures.

- **Follow-up:** Participants will have follow-up visits for up to 7 days post-dose as follows: Participants will return to clinic for visits on Study Days 4 and 7. Participants will receive a phone call on Study Day 5 to inquire about their general health.

Screening

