The PI or designee is responsible for administering and obtaining freely given consent in writing from all participants using the study-specific Informed Consent Form (ICF) prior to undergoing any screening procedures; this may also include consent to participate in the optional receptor occupancy substudy. Screening procedures will take place within 90 days prior to Day 1. The participant's eligibility (per Inclusion and Exclusion Criteria listed in Section 8), demographics, medical history, and concomitant medications will be recorded. Screening/baseline assessments will be performed, and participants will undergo blood draws for laboratory tests. Urine samples will also be collected. If eligibility criteria are met, and the participant is enrolled in the receptor occupancy substudy, a brain MRI will be performed for quantitative evaluation of PET scans. The MRI will be reviewed and participants with anatomical abnormalities or findings indicating neurological disease will be excluded. A full list of procedures and assessments is included in Table 3: Schedule of Study Events.

If a participant is rescreened, the original screening MRI and expert review of the images may be used for the rescreening provided the MRI was completed within 6 months prior to study drug administration. Similarly, neurologic examinations and questionnaires do not need to be repeated provided these assessments were completed within 6 months prior to study drug administration.

In-Patient Treatment Period

Eligible participants will be admitted to the HRU on either the evening prior to or the day of dosing (Study Day 1) depending on participant needs. Following final pre-treatment assessments, participants will receive their single dose of study drug administered orally. Dosing will be according to [Table 1](#).

Participants will remain as in-patients until discharge on Study Day 3 and will undergo safety assessments and close observation.

Blood samples will be obtained to assess safety and pharmacokinetics (PK). The timing for PK sample collection may be adjusted for subsequent cohorts based on data from the preceding cohorts.

Table 1: Treatment by Cohort

Cohort	Treatment	Number of Participants
1	10 mg BMS-984923	6
2	40 mg BMS-984923	6
3	70 mg BMS-984923	6
4	100 mg BMS-984923	6
5	150 mg BMS-984923	6

6	200 mg BMS-984923	6
---	-------------------	---

Follow-Up

Site will contact the participants via telephone on Study Days 5 to inquire as to their general health status.

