Prospective participants who are taking prohibited medications at the time of screening (listed in Section 8: Inclusion/Exclusion Criteria or [Appendix A](#)) may stop them in consultation with their physician, after signing the ICF and receiving instructions on the discontinuation of these medications. In this case, the prohibited medication must be discontinued prior to study drug administration as outlined in the Inclusion/Exclusion Criteria. The prospective participant must be willing to discontinue treatment and the PI must deem this to be feasible and safe. If a prospective participant is taking prohibited medication(s) at the time of screening, they may be considered eligible at the time of study drug administration (Visit 2, Study Day 1) provided no reintroduction of the prohibited medication is being considered, the appropriate time window since last administration has elapsed, and the participant continues to meet other eligibility criteria. Upon signing the ICF and enrollment into the study, participants must remain off prohibited medications until all assessments are completed in the study (Visit 5, Study Day 7), unless the PI determines that a medication is required for participant safety and/or to treat an (S)AE. The PI will first discuss starting prohibited medications with the medical monitor unless that cannot be done due to an immediate safety need.

Treatment Compliance

Treatment compliance with study drug during the treatment period is expected to be high, as participants will be dosed directly at the research unit under well-controlled conditions. The date and time of study drug administration, dose group, and quantity of study drug administered will be recorded on the source documents and CRF. Non-compliance with other aspects of the study protocol (e.g., use of prohibited medications, missed study visits) will be documented on the participant's source document and on the CRF.

Randomization and Blinding

This study is open-label and does not include a reference therapy, therefore there is no randomization.

Study Procedures

Participants will participate in the study for a total duration of up to 14 weeks. Visits will be scheduled at:

- Screening Visit 1 (Study Days -90 to -1)
- In-patient Treatment Visit 2 (Study Days 1, 2, and 3)
- Post Treatment Follow-up
 - Visits 3 (Study Day 4)
 - Visit 4 (Phone call on Study Day 5)
 - Visit 5 (Study Day 7)

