The goal is to collect adequate PET scan data for at least 2 participants per cohort. Up to four participants in each cohort may participate in the Receptor Occupancy Sub-study. These participants will undergo an MRI during screening and three [¹⁸F]FPEB PET Scans. PET scans will occur at screening (within 60 days of study drug administration), approximately 4 hours post-dose and approximately 24 hours post-dose. The timing of post-dose PET scans may be adjusted after review of human PK data collected in this study. Each participant may be asked to repeat up to one [¹⁸F]FPEB PET scan if a scan fails quality control for a total of up to four [¹⁸F]FPEB PET scans during the course of study participation. The baseline [¹⁸F]FPEB PET scan may be done after the inpatient and clinic follow-up visits if needed.

The rationale for enrolling up to four participants from each Cohort in the sub-study is to help ensure that quality [¹⁸F]FPEB PET scan data is collected at all three timepoints on at least two participants per cohort. This over-enrollment is necessary due to possibility of failed [¹⁸F]FPEB PET tracer synthesis and the time sensitive nature of the post-dose [¹⁸F]FPEB PET scans. The goal is to collect adequate PET scan data for 2 participants per cohort. We will not scan additional participants per cohort once adequate scan data has been captured.

MRI Procedures

Magnetic Resonance Imaging (MRI) will be performed for enrollment in the receptor occupancy substudy. To be screened by MRI, participants must meet all clinical eligibility criteria. MRI will be used for quantitative evaluation

of PET scans, to screen for anatomical abnormalities, and to screen for neurological disease. MRI exclusion criteria will consist of focal or global atrophy, evidence of chronic or acute cerebrovascular disease, any space occupying lesion or other indication of underlying pathology. All MRIs will be read by a local expert to ensure consistent interpretation. MRIs will take place at the Anlyan Center, [name].

MRI will be performed on a 3 Tesla system using pulse sequences selected to accommodate clinical reading, anatomical identification of VOIs, gray/white matter segmentation, and registration to a common space. Sequences will include:

- 3 Plane/Tri-Planar Scout
- Axial T2 Star/GRE
- Axial T2 FLAIR
- Axial fcMRI (Participant should have eyes OPEN)
- Sagittal 3D Accelerated MPRAGE/IRSPGR
- Axial DWI
- Axial DTI
- Axial PASL (eyes open)

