- Use of psychoactive medications (typical neuroleptics, narcotic analgesics, antiparkinsonian medications, systemic corticosteroids, or medications with significant central anticholinergic activity) within 2 weeks or 5 half-lives (whichever is greater) prior to study drug administration and for the duration of the trial.
- Use of medications with significant CYP1A2, 2D6, or 3A4 inhibitor or inducer activity (See [Appendix A](#) for a list of these medications) within 2 weeks or 5 half-lives (whichever is greater) prior to study drug administration and for the duration of the trial.
- Use of anticoagulants within 30 days or 5 half-lives (whichever is greater) prior to study drug administration and for the duration of the trial.
- Use of investigational amyloid lowering therapies within 2 months prior to study drug administration and for the duration of the trial.
- Use of another investigational agent within 30 days or 5 half-lives (whichever is greater) prior to screening and for the duration of the trial.
- Neutropenia defined as absolute neutrophils count of < 1,500/microliter.
- Thrombocytopenia defined as platelet count < 100,000/microliter.
- Clinically significant abnormalities in screening laboratories, including Aspartate aminotransferase (AST) >1.5 times ULN; Alanine aminotransferase (ALT) >1.5 times ULN; Total bilirubin >1.5 times ULN; Serum creatinine >2.0 times ULN.

Receptor Occupancy Substudy Eligibility Criteria

Inclusion Criteria

- Eligibility for and enrollment in Main Study
- Participant consent to the optional substudy

Exclusion Criteria

- Screening/baseline MRI scan with evidence of infection, infarction, or other focal lesions.
- Presence of multiple lacunes or lacunes in a critical memory structure in the brain as evidenced in an MRI.
- Any contraindications for MRI studies, including claustrophobia, the presence of metal (ferromagnetic) implants, metal fragments or foreign objects in the eyes, skin, or body or a cardiac pacemaker.
- Current or recent participation in research procedures involving radioactive agents such that the total radiation dose exposure to the participant in any given year would exceed the limits of annual and total dose commitment set forth in the US Code of Federal Regulations (CFR) Title 21 Section 361.1.

9. How will **eligibility** be determined, and by whom?

See above question for specific eligibility criteria. Eligibility will be determined by the PI based on review of Inclusion/Exclusion criteria.

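### The anticoagulant washout is counted back from dosing only, so a baseline PET arterial line placed up to 60 days earlier can come before the stop date or before the washout is complete

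*Combined protocol and SAP*

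**What the plan says.** **Anticoagulants.** The Participant Exclusion Criteria (Section I, item 8) list "Use of anticoagulants within 30 days or 5 half-lives (whichever is greater) prior to study drug administration and for the duration of the trial". Neither the substudy criteria in the same item nor the arterial-catheter text in items 10 and 11 contains a further anticoagulant rule.

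**Stopping during screening.** Under Concomitant Medications (item 4), people taking a prohibited drug at screening "may stop them in consultation with their physician, after signing the ICF and receiving instructions on the discontinuation of these medications", and then "the prohibited medication must be discontinued prior to study drug administration as outlined in the Inclusion/Exclusion Criteria". Overall Study Design puts that washout inside screening: "Patients have 90 days from the time of signing informed consent to complete their screening assessments and, if needed, their washout period". For the end of the restriction, Concomitant Medications says that "participants must remain off prohibited medications until all assessments are completed in the study (Visit 5, Study Day 7", with an exception for safety needs.

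**The arterial line.** The baseline scan may take place up to 60 days before dosing or, if necessary, after the follow-up visits (Table 3, footnote 9; Receptor Occupancy Substudy). PET Scan Procedures calls for a radial artery catheter before the scan, and Section VI, item 2 counts three lines for three scans, so the baseline scan has one. Item 11 asks participants to avoid aspirin and other NSAIDs for 7-10 days before insertion and 7-10 days after removal.

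**Checks that bear on the order of events.** On laboratory tests: "The screening laboratory tests must be completed within 30 days prior to Day 1". On the MRI, the Screening section says: "If eligibility criteria are met, and the participant is enrolled in the receptor occupancy substudy, a brain MRI will be performed". MRI Procedures adds: "To be screened by MRI, participants must meet all clinical eligibility criteria".

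**The concern.** The washout and the puncture run on different clocks. The washout is dated to dosing, but a substudy participant's first arterial puncture can come weeks before dosing. Someone who complies fully with the written rule could still be taking an anticoagulant, or have only recently stopped, when the baseline line goes in.

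What is at stake is participant safety, not inference. Item 10 names bleeding and hematoma among the risks of the catheter. The puncture is for research only, in healthy people aged 50 to 80 who get no direct benefit. The plan already times aspirin and NSAIDs to the line, so leaving anticoagulants off that clock looks like an oversight in drafting.

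**Working it through.** The plan states no derived figure to reproduce; the check is date arithmetic. Day -n here means n days before dosing.

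**Inputs**
- Required washout W = max(30, 5 × half-life) days before dosing (Section I, item 8).
- Earliest pre-dose baseline line: 60 days before dosing (Table 3, footnote 9).
- Screening period: 90 days, washout included (Overall Study Design).
- Anticoagulant half-lives: not in the documents. The values below are assumptions.

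**Formula.** Let S be the days before dosing on which the drug is stopped (the rule needs S ≥ W) and L the days before dosing on which the line is placed (1 to 60). Time off drug at the line is S - L.
- S - L below 0: the line comes before the stop.
- S - L from 0 to below W: the washout is incomplete.
- S - L of W or more: the washout is complete.

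**Results when the 30-day window governs (half-life 6 days or less, W = 30)**

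| Drug stopped (S) | Line before stop | Washout incomplete | Washout complete |
|---|---|---|---|
| 30 | Days -60 to -31 (60 - 30 = 30 days) | Days -30 to -1 (30 days) | none |
| 45 | Days -60 to -46 (60 - 45 = 15 days) | Days -45 to -16 (30 days) | Days -15 to -1 (15 days) |
| 60 | none | Days -60 to -31 (30 days) | Days -30 to -1 (30 days) |
| 90 | none | none | Days -60 to -1 (60 days) |

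Examples for S = 30: a line at Day -60 precedes the stop by 60 - 30 = 30 days; a line at Day -14 follows it by 30 - 14 = 16 days.

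**Longer assumed half-lives, stopping on the last permitted day (S = W).** Days on which the line could precede the stop = max(0, 60 - W):
- 8 days: W = 40, 20 days
- 10 days: W = 50, 10 days
- 12 days or more: W ≥ 60, 0 days

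In each case every pre-dose line still falls inside the washout, because S - L is less than W for any L of 1 or more.

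**Which lines.** The two post-dose lines, about 4 and 24 hours after dosing, follow a washout completed by dosing. Only the baseline line, one of three, is affected.

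**How many people.** The target is two per cohort: 2 × 4 = 8 for the 10-100 mg cohorts, or 2 × 6 = 12 if 150 and 200 mg are scanned. Up to four per cohort may join, so at most 4 × 4 = 16 or 4 × 6 = 24 could have a baseline line. How many would be on an anticoagulant at screening is not given.

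**The case against.** The best reply is that eligibility is settled before imaging. The MRI requires all clinical criteria to be met, and screening laboratory tests must fall within 30 days of Day 1. In the ordinary order (laboratory tests, MRI, PET) the baseline scan would fall in Days -30 to -1. The substudy also requires main-study eligibility, and Concomitant Medications makes a washout candidate eligible only once the window since the last dose has elapsed.

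This makes an early line unlikely but does not rule it out. The eligibility checks are attached to the MRI and not to the PET. The criterion they test is itself dated to dosing, so use at Day -45 does not breach it. If substudy eligibility meant that the Day 1 check had to be passed first, no pre-dose baseline scan could ever be done. Nor does a scan in Days -30 to -1 settle the matter: the stop date has been reached, but the washout may not be complete.

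Three further objections stand in part:
- **Why 30 days?** The plan does not say that anticoagulants are excluded because of the line; the exclusion also covers participants who have none. The 30-day interval is the plan's own washout, borrowed here. Nothing in the documents shows it to be the interval an arterial puncture needs.
- **Practical safeguards.** Medications are recorded, the investigator must judge stopping feasible and safe, and experienced operators place the line. These lower the risk. The venous fallback is offered when a line cannot be placed or maintained, so it is not an anticoagulant safeguard.
- **Longer interruption.** Counting back from an early line would keep a participant off a prescribed drug for longer. This is a real cost, and the fix has to allow for it.

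A reader might also infer that a baseline scan done after follow-up escapes the ban, because Concomitant Medications names Visit 5. The documents do not support that: the exclusion runs for the whole trial, the off-drug rule lasts until all assessments are done, and a late scan is one of those assessments.

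**Conclusion.** The gap in the written rule is real and minor. Under the 30-day window, someone who stops an anticoagulant on the last permitted day could have the baseline line before the stop date on up to 30 calendar days, and with an incomplete washout on the remaining 30 pre-dose days. Earlier stopping shrinks both periods, and stopping 90 days before dosing removes them.

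These are days on which the text permits a line. They do not measure bleeding risk, and a reader should not infer that participants will have lines placed while anticoagulated. That would take an anticoagulant user among healthy volunteers, a decision to join the optional substudy, an early baseline scan, and no one acting on the medication record. Very few people, possibly none, would meet all of these. Sample size and the descriptive analyses are unaffected.

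The conclusion rests on the dosing-dated wording and on the permission to stop after consent. The half-lives are assumed, and the number of anticoagulant users is unknown.

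**What to change.** Add one item to the Receptor Occupancy Substudy exclusion criteria, along these lines:

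> No arterial line is placed until the washout required by the main-study anticoagulant exclusion has been completed, counted back from insertion of that line. The participant stays off anticoagulants until the last arterial line has been removed.

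Add a scheduling note: for anyone who needs a washout, do the baseline scan late in screening or leave them out of the optional substudy. This keeps the interruption short. With the 30-day window, time off drug through Day 7 is about 30 + 7 = 37 days under the present rule. Counted back from the line it would be about 60 + 30 + 7 = 97 days for a line at Day -60, 14 + 30 + 7 = 51 for Day -14, and 1 + 30 + 7 = 38 for Day -1. A Day -60 line only just fits the 90-day screening period (60 + 30 = 90) and should be avoided for these people.

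Extending the Visit 5 label in Concomitant Medications to cover a later baseline scan would help clarity but is not essential.

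The cost is one added criterion and one note. A few candidates would be scanned later or not at all, or would be off an anticoagulant somewhat longer.

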
10. **Risks:** Describe the reasonably foreseeable risks, including risks to subject privacy, discomforts, or inconveniences associated with subjects participating in the research.

Risks Associated with BMS-984923

BMS-984923 has not previously been administered to humans. Toxicology studies have been completed in rat and non-human primate, with no adverse effects at the doses comparable to the planned doses. At doses higher than those planned for this study in humans [see Investigator Brochure (IB) section 4.3.2.1], serious adverse effects related to drug accumulation were observed in rats receiving repeated doses greater than 15 mg/kg/day. These adverse effects were gradual in onset over days and were manifest by lethargy, generalized stress responses, and death without organ specific or acute toxicity. This constellation of serious adverse effects was reversed after cessation of daily 100 mg/kg/day administration. There was no evidence for acute onset cardio-respiratory or CNS toxic effects. In order to mitigate the risk of similar adverse effects in humans, our planned maximal dose is well below the human equivalent of the rat and monkey no observed adverse effect level (NOAEL). Please refer to the Investigator Brochure (IB) for more detailed information on toxicology investigations.

Risks Associated with Electrocardiograms (ECGs)

There is no pain or discomfort during an ECG; however, removing the pads may cause some irritation to the skin.

Risks Associated with Blood Drawing and IV Line Insertion

Drawing blood and inserting an intravenous line (IV) into an arm vein are safe and standard medical procedures. Sometimes a bruise will occur at the puncture site and rarely a blood clot or infection will occur in the vein. Certain individuals may feel light-headed during venipuncture. A total of approximately 70 mL (~5 tablespoons) of blood will be collected from each participant during this study. A total of approximately 140 mL (~10 tablespoons) of blood will be collected from each participant in Cohort 4 and subsequent dose cohorts.

Psychological Stress

The tests used to assess the participant's mental performance may sometimes cause anxiety or fatigue.

Risks Associated with Unanticipated Events

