To minimize the potential risks of BMS-984923, participants with unstable medical conditions will be excluded. At doses higher than those planned for this study in humans, serious adverse effects related to drug accumulation were observed in rats. These adverse effects were gradual in onset over days, were reversed by cessation of daily administration, and were manifest by lethargy and generalized stress responses without organ specific or acute toxicity. There was no evidence for acute onset cardio-respiratory or CNS toxic effects. In order to mitigate the risk of similar adverse effects in humans, our planned maximal dose is well below the human equivalent of the rat and monkey NOAEL. Risks will be further minimized by the safety assessments detailed in the protocol, including neurological checks using the GCS, physical/neurological examinations, vital signs, ECGs, and clinical laboratories (See Table 3: Schedule of Study Events). Finally, safety of participants will be further enhanced according to the provisions of the Data Safety Monitoring Plan (DSMP).

Participants in the receptor occupancy sub-study will undergo increased monitoring while in the PET scanner. The monitoring will continue as described in the protocol and a PET technician and research coordinator will also be monitoring the participant for signs of physiologic or psychiatric distress during the scan. In addition, participants will have continuous blood pressure and heart rate monitoring by arterial line.

Risks Associated with Blood Drawing and IV Line Insertion

To minimize risks of associated with blood draws and IV line insertion, experienced medical personnel will do all the blood-drawing procedures.

Risks Associated with MRI

To minimize risks associated with MRI, the MRI's will be conducted by experienced personnel at The Anlyan Center at Yale. All participants will complete the MRI safety questionnaire prior to having the MRI.

Risks Associated with Psychological Stress

To minimize psychological stress, appropriate breaks will be provided to participants as needed

Minimization of Risks Associated with Receptor Occupancy Substudy

Risks Associated with MRI

To minimize risks associated with MRI, the MRI's will be conducted by experienced personnel at The Anlyan Center at Yale. All participants will complete the MRI safety questionnaire prior to having the MRI.

Risks Associated with Arterial Catheter

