Dose escalation decisions will be determined with the following approach. At the completion of each cohort, 0-72 h PK data will be used to assess the plasma exposure derived from the area under the curve (AUC) from 0-24 h. Our dose escalation decisions will be based on the human data relative to the rat 28 day GLP toxicology study to determine maximal NOAEL. In that study, the plasma exposure at NOAEL based on AUC (0-24h) was 192,000 ng*h/mL (see IB). Furthermore, the plasma exposure in corresponding Cynomolgus study was similar at 169,000 ng*h/mL.

The maximal doses for each cohort will be 10, 40, 70, 100, 150 and 200 mg. The human equivalent dose derived from the NOAEL dose in the 28D toxicology study in the most sensitive species (rat) is 140 mg. Thus, the starting dose is less than 10% of the 140 mg amount. Dose escalation in cohorts 2-6 will follow the plan above, but will be decreased based on the observed plasma exposure of the AUC (0-24 h) as detailed in the schedule below. The dose escalation for the next cohort will be based on the most recent cohort observed PK analysis as follows:

If plasma $AUC_{0-24h} < 24,000 \text{ ng}^*\text{h}/\text{ml}$ (12.5% NOAEL), then dose increase according to schedule
 If plasma $AUC_{0-24h} 24,000-48,000 \text{ ng}^*\text{h}/(12.5-25\% \text{ NOAEL})$, then dose increase maximum of 2 fold
 If plasma $AUC_{0-24h} 48,001-96,000 \text{ ng}^*\text{h}/\text{ml}$ (25-50% NOAEL), then dose increase maximum of 1.5 fold
 If plasma $AUC_{0-24h} 96,001-120,000 \text{ ng}^*\text{h}/\text{ml}$ (50-67.5% NOAEL), then dose increase maximum of 1.3 fold
 If plasma $AUC_{0-24h} > 120,000 \text{ ng}^*\text{h}/\text{ml}$ (>67.5% NOAEL), then stop escalation

Any serious adverse events or other safety concern might also constitute a rationale to stop or reduce escalation.

Criteria for intervention discontinuation

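### The risk text puts the maximal dose well below the rat NOAEL equivalent, but cohorts 5 and 6 are planned at up to 107% and 143% of it

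*Combined protocol and SAP*

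**What the plan says.** Section I, item 10 (Risks Associated with BMS-984923) reports that "serious adverse effects related to drug accumulation were observed in rats receiving repeated doses greater than 15 mg/kg/day", with lethargy, stress responses and death. It then gives the mitigation: "our planned maximal dose is well below the human equivalent of the rat and monkey no observed adverse effect level (NOAEL". Item 11 (Minimizing Risks) repeats it: "our planned maximal dose is well below the human equivalent of the rat and monkey NOAEL". Both items attribute the rat effects to accumulation, with gradual onset over days and reversal when daily dosing stopped. Item 11 also points in general terms to the monitoring plan. Neither item mentions AUC or exposure.

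Item 12 (Safety Assessment and Dose Escalation Decisions) gives the benchmark: "The human equivalent dose derived from the NOAEL dose in the 28D toxicology study in the most sensitive species (rat) is 140 mg". The same paragraph sets out the planned schedule, whose last two steps lie above that figure: "The maximal doses for each cohort will be 10, 40, 70, 100, 150 and 200 mg". Table 1 and the Treatment Assignment text in item 4 list the same six doses. Item 12 adds that escalation in cohorts 2 to 6 "will be decreased based on the observed plasma exposure of the AUC (0-24 h) as detailed in the schedule below". The reference exposures are, for the rat, that "the plasma exposure at NOAEL based on AUC (0-24h) was 192,000 ng*h/mL" and, for the monkey, that "the plasma exposure in corresponding Cynomolgus study was similar at 169,000 ng*h/mL". The rule allows the scheduled increase below 24,000 ng*h/mL, caps it at 2-fold, 1.5-fold and 1.3-fold in the next three bands, and stops escalation above 120,000.

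**The concern.** Items 10 and 11 say that the top planned dose is comfortably under the rat benchmark. Item 12 gives that benchmark as 140 mg and plans two cohorts above it. For the rat, then, the stated margin points the wrong way at the top of the schedule.

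This matters because the study is first-in-human and these are the two items where an IRB looks for drug risk and how it is reduced. The protection for doses above 140 mg is conditional: they open only if observed human exposure is low enough. A reader of items 10 and 11 sees an unconditional dose margin, is not told that planned doses exceed 140 mg, and is not told that the AUC rule is what limits them.

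**Working it through.** **Inputs**, all from Section I, item 12: rat human equivalent dose 140 mg; cohort maxima 10, 40, 70, 100, 150 and 200 mg; NOAEL AUC(0-24h) 192,000 (rat) and 169,000 (monkey) ng*h/mL; the escalation bands and caps above. The 140 mg itself cannot be re-derived, because the documents give neither the conversion factor nor a reference body weight.

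**Step 1: reproduce the plan's own ratio.** Item 12 says the starting dose is under 10% of 140 mg. 10/140 = 7.1%, which agrees. The protocol therefore uses 140 mg as a dose benchmark itself.

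**Step 2: apply the same ratio to every cohort.**

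| Planned dose | Dose / 140 mg |
|---|---|
| 10 mg | 7.1% |
| 40 mg | 28.6% |
| 70 mg | 50.0% |
| 100 mg | 71.4% |
| 150 mg | 107.1% |
| 200 mg | 142.9% |

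The planned maximum is 60 mg above the rat equivalent. Cohorts 5 and 6 hold 6 participants each, so up to 12 of 36 are affected if both open at full dose.

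**Step 3: exposure at the stop limit.** 120,000/192,000 = 62.5% of the rat value, and 120,000/169,000 = 71.0% of the monkey value. (Item 12 labels 120,000 as 67.5% of the NOAEL. That is a separate slip.)

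**Step 4: how far the rule can carry the dose.** Assume dose-proportional PK and cohort-level AUC, and let s be AUC per mg, so AUC = s × dose. Each next dose is the smaller of the scheduled dose and the capped multiple.

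- If 140 mg gave exactly the rat NOAEL exposure, s = 192,000/140 = 1,371. The rule then gives 10 mg (13,714), 40 mg (54,857; cap 1.5), 60 mg (82,286; cap 1.5) and 90 mg (123,429), and stops. No dose above 140 mg opens.
- s = 960: 100 mg gives 96,000, so 150 mg is allowed. It gives 144,000, and escalation stops.
- s = 800: 150 mg gives 120,000, so the cap is 1.3 and the next dose is 195 mg, giving 156,000.
- s = 640: 150 mg gives 96,000, so the cap is 1.5 and 200 mg is allowed, giving 128,000.

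| Dose reached | Largest s that allows it | s / 1,371 | Largest projected AUC | % of rat 192,000 | % of monkey 169,000 |
|---|---|---|---|---|---|
| 150 mg | 960 | 70% | 144,000 | 75% | 85% |
| 195 mg | 800 | 58% | 156,000 | 81% | 92% |
| 200 mg | 640 | 47% | 128,000 | 67% | 76% |

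The largest projected AUC the rule permits after cohort 1 is 1.3 × 120,000 = 156,000.

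**Step 5: where the sentence would be right.** With a maximum of 100 mg the ratio is 71%, and the statement would be defensible. The first four doses in Table 1 end at 100 mg. The DSMB text in item 12 and the Targeted Enrollment text in Section III still describe four cohorts. The sentence may simply not have been updated when cohorts were added; this is an inference that the documents do not state.

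**The case against.** The strongest reply is that the sentence doses nobody. Item 12 governs. Its doses are maxima, they are cut back on observed AUC, and each escalation needs agreement from the PI, medical monitor, DSMB and IND holder. Item 12 prints 140 mg beside the 150 and 200 mg doses, and item 11 points to the monitoring plan, so an IRB or DSMB reading the whole protocol has the facts. This stands as a limit: the fault is an inaccurate risk statement, not unsafe dosing. It does not cure the statement, because the disclosure in item 12 is what contradicts it.

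A second reply is that the human equivalent may be meant as exposure, since escalation is run on AUC and the monkey comparison is given only as AUC. On that reading 200 mg itself projects to at most 67% of the rat value and 76% of the monkey value; 81% and 92% arise at other doses, such as 195 mg. Those figures are correct, and whether they count as well below is a judgement. But the sentence compares a dose with a human equivalent in the dose terms that item 12 uses, and the documents hold no human PK that could support an unconditional exposure margin in advance.

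Third, 140 mg comes from 28-day repeated dosing, the rat effects were tied to accumulation, and this trial gives one dose. That may well justify exceeding 140 mg. The protocol neither says that it is exceeded nor makes that argument.

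**Conclusion.** The concern holds. On a dose basis the statement in items 10 and 11 is wrong for the rat in two of six planned cohorts: 107% at 150 mg and 143% at 200 mg, against a stated equivalent of 140 mg. This part rests only on figures in the protocol.

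The exposure results rest on three assumptions: dose-proportional PK, cohort-level AUC (individuals may differ), and that 140 mg and 192,000 ng*h/mL describe the same rat dose. Under them, doses above 140 mg open only if human AUC per mg is at most 70% of the implied 1,371, and projected cohort AUC stays below both NOAEL exposures. The finding therefore does not show that NOAEL exposure would be exceeded. The monkey half of the sentence cannot be checked, because no monkey human-equivalent dose is given. The separate statement under Criteria for intervention discontinuation, that planned doses lie below the equivalent of the repeated doses that caused the rat effects, is a different claim and is not disputed.

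**What to change.** Before cohort 5 opens, replace the sentence in Section I, items 10 and 11, with text that:

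- gives the dose margins against the 140 mg rat equivalent: 71% at 100 mg, 107% at 150 mg and 143% at 200 mg;
- states that doses above 140 mg open only under the AUC(0-24h) rule in item 12, with the projected margins against 192,000 (rat) and 169,000 (monkey) ng*h/mL and the PK assumption behind them;
- turns the accumulation rationale into an explicit argument for why a single dose may exceed a 28-day repeat-dose equivalent;
- gives the monkey human-equivalent dose, or drops the monkey from the sentence;
- says so, if the equivalence is meant on an exposure basis.

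The IRB and DSMB should review cohorts 5 and 6 on the corrected text, and the consent form should be checked for the same statement. The cost is amendment wording in two items and that review. Doses, sample size and procedures do not change; the stated margin becomes less favourable.
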